This study is a preliminary randomized control trial evaluating a 9-week diet and lifestyle intervention on quality of life, patient-reported symptoms, and biomarkers associated with methylation. We will recruit forty-eight participants with 24 randomized to each study group. Refer to Figure 1 for an overview of the study flow.

Figure 1. Study Flow Overview

D.2 Study Intervention

Study participants will be randomized into an intervention or control group. The intervention group will undergo a 3-week washout period following the discontinuation of any non-medically required nutrition or herbal supplements. The intervention group will follow detailed diet and lifestyle recommendations over a 9-week period. Two webinars at the start of the

Protocol

Study Title: Methylation Diet and Lifestyle (MDL) Study

PI: [name], ND, MPH and [name], ND

IRB #: RB100217

Approval Date: 2.9.18

Ver. 1.1

intervention phase will provide information to participants on proper food and exercise choices, as well as how to access and use the required electronic resources (apps).

The control group will undergo the same testing measures as the intervention group, but will not have access to the education information or be instructed to change diet or lifestyle factors. They will have access to the information after the study is complete.

D.2.1 Diet Recommendations

Specific dietary guidelines will be outlined for participants and should include the following:

Per week	Per day

3 servings of liver
 
 • (1 serving = 3 oz) • Choose preferably organic liver 
5-10 eggs
 
 • Ideally free-range, organic, omega-3 enriched 	
2 cups of dark leafy greens
 
 • Measured raw, chopped, and packed • Including kale, Swiss chard, collards, spinach, dandelion, mustard greens • Does not include salad greens such as romaine, iceberg, Spring mix 
2 cups cruciferous vegetables
 
 • Measured raw, chopped, and packed • Including broccoli, cabbage, cauliflower, Brussels sprouts, bok choy, arugula, kale, watercress, rutabaga, kohlrabi, radish, turnip
General	

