Not all foods recommended and consumed during the study intervention may be captured by VioScreen. An additional food frequency questionnaire (FFQ), with approximately 250 foods and beverages, was created to assess consumption. It has been designed to be consistent with the validated block Brief FFQ by NutritionQuest. This will be administered electronically via RedCap online database to all study participants at Visits 1, 2, and 3.

D.2.7.5. Adherence phone calls

Participants will be contacted via phone once per week during the first 4 weeks of the study and every other week for the remainder of the study. Designated health coaches will assess for adherence to the study intervention including dietary, stress management, and exercise recommendations. Participants will be able to ask questions pertaining to the study intervention.

Refer to Appendix B for detailed script of these phone calls.

Protocol

Study Title: Methylation Diet and Lifestyle (MDL) Study

PI: [name], ND, MPH and [name], ND

IRB #: RB100217

Approval Date: 2.9.18

Ver. 1.1

D.3 Description of Participant Population

D.3.1. Participant Characteristics

Sample size: n=48

We will enroll and randomize up to 48 people which will allow for 20% attrition such that we have an evaluated sample size of 40 to allow for withdraws or dropouts.

Age: 50-72

Gender: Males only

Minorities: all racial and ethnic backgrounds will be recruited from the general population without preference or discrimination.

Vulnerable Populations (e.g. children, pregnant women, cognitively impaired): No vulnerable populations will be enrolled.

D.3.2. Inclusion and Exclusion Criteria

Individuals must meet the following participation criteria:

Inclusion criteria:

- Males, ages 50-72
- Willing to adhere to 9 weeks of a dietary and lifestyle program including specific nutrition and exercise guidelines
- Willing to avoid any over-the-counter medications, supplements or herbal products for the length of the study, except short-term use (<1 week) use at least 1 week before scheduled study visits
- Willing to have blood drawn three times and abstain from food or beverage intake for 10-12 hours before blood draws
- Willing to provide saliva samples
- Willing to track food intake, sleep, stress management techniques, and exercise daily
- Willing to drink a nutrient-enriched beverage and take a encapsulated probiotic daily
- Willing and able to use electronic devices and connect to the internet

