The following procedures, evaluation and/or assessments will be obtained at Study Visit 2:

- Weight
- Vital signs including heart rate, blood pressure, respiration rate and temperature
- Questionnaires including Lifestyle Habits, PROMIS-29, MYMOP, MSQ, and NUNM Adverse Events, VioScreen
- Blood draw to collect 2 tubes of blood
- Saliva sample
- If in intervention group, will receive study supplements for remaining 4 weeks of study
- Case report form completed by study staff

Study Visit 3 (Week 9)

The following procedures, evaluation and/or assessments will be obtained at Study Visit 3:

- Weight
- Waist-to-hip ratio will be calculated as previous defined in Study Visit 1
- Vital signs including heart rate, blood pressure, respiration rate and temperature.
- Questionnaires including Lifestyle Habits, PROMIS-29, MYMOP, MSQ, and NUNM Adverse Events, VioScreen
- Blood draw to collect 2 tubes of blood
- Saliva sample
- If in intervention group, return unused supplements
- Case report form completed by study staff

Protocol

Study Title: Methylation Diet and Lifestyle (MDL) Study

PI: [name], ND, MPH and [name], ND

IRB #: RB100217

Approval Date: 2.9.18

Ver. 1.1

D.5.9. Educational Webinars

Weekly, live webinars will provide information on the diet, exercise, stress management, and lifestyle recommendations. Prior to initiating any of these changes, an introductory webinar will provide an overview of the study intervention. An additional webinar will provide detailed instruction on how to access and utilize two electronic applications – MBody360 and Stress Free Now. All webinars will be delivered via Zoom, a free online communication application.

Refer to Appendix C for detailed information on webinar content

D.6. Study Withdrawal and/or Early Termination

Participants will be informed that they have the right to withdraw from the study at any time, without affecting their relationship with NUNM. Participants may also be discontinued from the study if the investigators determine it is in the best interest of the participant.

Information about study withdrawal or premature discontinuation from the study will be captured throughout the study. Study withdrawal or premature discontinuation will be categorized as follows:

- Participant began taking an excluded medication or supplement

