- The Principal/Clinical Investigator decided that withdrawal/discontinuation was in the best interest of the participant due to an adverse event, non-compliance, or another reason
- The participant requests withdrawal from the study for reasons other than above
- The participant failed to return for study visits

If a participant withdraws before the second visit, they will be replaced, however participants who withdraw between the second and third visits will not be replaced. Every effort will be made to collect a final salivary sample and all final labs from all participants, even if they withdraw from the study early.

D.7. Study Products

D.7.1. PhytoGanix (tropical fruit flavor)

Organic Superfruits & Greens Powder Drink Mix is a food-based phytonutrient blend designed to support intestinal health and immune function.

Protocol

Study Title: Methylation Diet and Lifestyle (MDL) Study

PI: [name], ND, MPH and [name], ND

IRB #: RB100217

Approval Date: 2.9.18

Ver. 1.1

Serving Size: 1 Scoop (10.4 grams)

Ingredient	Amount per serving
Calories	40
Total Carbohydrate	9 g
Dietary Fiber	1 g
Sugars	1 g
Protein	1 g
Vitamin C (as ascorbic acid)	100 mg
Calcium	20 mg
Iron	1.4 mg
Sodium	30 mg
Organic Seed and Prebiotic Blend:	5.53 g
Isomalto-Oligosaccharide, Flax Seed Powder, Chia Seed Powder, Quinoa (Chenopodium quinoa Willd.) Sprout Powder	
Organic Veggie Blend:	2.35 g
Spirulina Whole Algae Powder, Carrot Root Powder, Broccoli Head Powder, Cauliflower Head Powder, Spinach Leaf Powder, Parsley Leaf Powder, Bamboo Shoot Extract, Beet Root Powder	
Organic Fruit Blend:	1.2 g
Apple Fruit Powder, Pineapple Fruit Powder, Strawberry Fruit Powder, Raspberry Fruit Powder, Blackberry Fruit Powder, Blueberry Fruit Powder	
Herbal Support Blend:	300 mg
Milk Thistle Seed Extract, Turmeric Rhizome Extract, Green Tea Leaf Extract, Reishi Mushroom Whole Plant Powder, Maitake Mushroom Whole Plant Powder, Shiitake Mushroom Whole Plant Powder, Japanese Knotweed Root Extract, Quercetin Dihydrate, Organic Maca Root Powder, Organic Cassia Bark Powder, Dong Quai Root Powder, Ginger Root Powder, Garlic Bulb Powder	
Enzyme Blend (including protease, amylase, lipase, and cellulase)	200 mg
Lactobacillus acidophilus VK3 Strain	200 mg

Protocol

Study Title: Methylation Diet and Lifestyle (MDL) Study

PI: [name], ND, MPH and [name], ND

IRB #: RB100217

Approval Date: 2.9.18

Ver. 1.1

D.7.2. UltraFlora Intensive Care

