Serious Adverse Event (SAE): Any untoward medical occurrence that results in death, is life-threatening, requires inpatient hospitalization or prolongation of existing hospitalization, results in persistent or significant disability or incapacity, or results in a congenital anomaly or birth defect. Other important medical events requiring medical or surgical intervention to prevent a serious outcome would also be considered SAEs.

Unanticipated Problems (UP): Any incident, experience, or outcome that meets all of the following criteria: 1) unexpected (in terms of nature, severity, or frequency) given (a) the research procedures that are described in the protocol-related documents, such as the IRB-approved research protocol and informed consent document; and (b) the characteristics of the subject population being studied; 2) related or possibly related to participation in the research and 3) suggests that the research places subjects or others at a greater risk of harm (including physical, psychological, economic, or social harm) than was previously known or recognized.

G.4. Statistical Analysis

PROMIS 29 T-scores will be presented as mean (SD), for each group at each of the three data collection time points. For the primary aim, we will compare changes in PROMIS-29 T-scores between groups, using a linear mixed model with random intercept to test for a Group*Visit interaction. If there is a significant main effect, we will also present uncorrected contrasts comparing changes from baseline to Week 5, and from baseline to Week 9, between groups.

Although PROMIS T-scores are not particularly susceptible to extreme outliers, data will be examined for any outlying PROMIS scores or changes in PROMIS scores. If these scores are deemed to be in error, then they will be treated as missing in all analyses. Otherwise, scores

Protocol

Study Title: Methylation Diet and Lifestyle (MDL) Study

PI: [name], ND, MPH and [name], ND

IRB #: RB100217

Approval Date: 2.9.18

Ver. 1.1

will be retained in the main analysis; but we will conduct separate sensitivity analyses to test for effects of outlying data on results.

Mixed models incorporate all available data, without excluding any participants from analysis. Nevertheless, any participants who have baseline data only will be excluded from analysis. As an exploratory follow-up analysis, we will re-analyze changes from Week 1 to Week 9, using data from completers only.

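### The primary mixed-model analysis drops randomised men with a baseline PROMIS-29 only, although the named model can use them: a minor point with a free fix

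*Protocol*

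**What the plan says.** Protocol G.4 compares PROMIS-29 T-scores between groups "using a linear mixed model with random intercept to test for a Group*Visit interaction", with follow-up contrasts of change from baseline to Week 5 and to Week 9. It remarks that a mixed model draws on every available observation and needs nobody left out. The next sentence makes an exception: "any participants who have baseline data only will be excluded from analysis". No reason is given. The only other analysis population in G.4 is an exploratory set of completers, which is narrower.

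Randomisation follows the screening visit (D.5.1), and PROMIS-29 is first taken at Study Visit 1 (D.5.8 and Table 4). A man with baseline data only has therefore already been randomised.

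For men who withdraw, D.6 says "Every effort will be made to collect a final salivary sample and all final labs from all participants". PROMIS-29 is not named there, although it is among the scheduled Visit 3 items: "Questionnaires including Lifestyle Habits, PROMIS-29, MYMOP, MSQ, and NUNM Adverse Events, VioScreen".

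**The concern.** Under the exception, whether a man counts in the primary analysis depends on what happens after he is allocated. Allocation cannot be hidden in a wait-list design, and the demands differ by arm. Only the intervention arm has the washout (D.5.7) and the diet, exercise, stress and supplement programme. The control group "will not have access to the education information or be instructed to change diet or lifestyle factors". Early loss could therefore differ between arms. If it is also related to the baseline score, the men who remain are a selected group whose scores drift back towards the mean, and that drift enters the estimated treatment difference. A random-intercept model given the leavers' baseline scores can adjust for such selection. With those scores removed it cannot. The rule is stated outright in the protocol, so it is not a detail left to a later analysis plan.

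**Working it through.** **Inputs.** From the protocol: 24 men per group (D.1), 40 evaluable (D.3.1, taken here as 20 per arm), three visits and a random-intercept model (G.4). The protocol gives no SD, correlation, early-loss rate or power calculation, so it has no figure of its own to reproduce here. Assumed: T-score SD 10; correlation rho between visits 0.5 or 0.7; a leaver has baseline only; the chance of leaving follows a logistic curve in the standardised baseline score z.

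**Bias when baseline-only men are excluded.** Among stayers in one arm, the expected change is shifted by (rho − 1) × SD × E[z | stay]. The bias in the treatment difference is this shift in the intervention arm minus the shift in the control arm.

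**Standard error.** The variance of a change is 2 × SD² × (1 − rho). With 20 per arm the standard error is sqrt(2 × 100 × (1 − rho) × 2/20), which is 2.45 at rho 0.7 and 3.16 at rho 0.5.

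**All early loss in the intervention arm.** Absolute bias in T-points, rho 0.7 / rho 0.5:

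| Log-odds of leaving per SD | 1/6 leave | 1/4 leave |
|---|---|---|
| 0 | 0 / 0 | 0 / 0 |
| 0.25 | 0.12 / 0.21 | 0.19 / 0.31 |
| 0.5 | 0.24 / 0.40 | 0.36 / 0.60 |
| 1 | 0.44 / 0.73 | 0.64 / 1.07 |
| 2 | 0.67 / 1.12 | 0.96 / 1.59 |

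Example: 1/4 leaving, log-odds 0.5, rho 0.5. E[z | stay] is −0.120 in size and sign when higher scorers leave, so the bias is 0.5 × 10 × 0.120 = 0.60, and 0.60/3.16 = 0.19 standard errors.

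- At log-odds 0.25 to 0.5 the range is 0.12 to 0.60 points, 0.05 to 0.19 standard errors, with two-sided type I error 5.0 to 5.4%.
- The worst cell is 1.59 points, 1.59/3.16 = 0.50 standard errors, with type I error about 8%.

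**Loss in both arms.** With 3 intervention and 1 control leaver, at log-odds 0.25 to 0.5, the bias is 0.06 to 0.20 points (0.20/3.16 = 0.06 standard errors). With equal loss that depends on baseline in the same way in both arms, the two shifts cancel.

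**Fitting the model.** In a REML simulation of the random-intercept model (24 per arm, 20,000 trials per cell), exclusion gave a mean bias of 0.13 to 0.58 at log-odds 0.25 to 0.5, and 1.58 at most. With the baseline-only men kept, the mean bias was within 0.05, rejection was 4.7 to 5.3%, and the mean standard error was 0 to 2% smaller. A separate simulation with 4% control and 25% intervention loss, strongly tied to baseline, gave a bias of 0.72 to 1.69 with exclusion and at most 0.04 without it.

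**What keeping them does not do.** In that second simulation, when leaving depended on the unseen change, keeping the men reduced the bias only from 2.30 to 1.72 (25%) at rho 0.5 and from 1.59 to 1.35 (15%) at rho 0.7.

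**The D.6 data request, a separate matter.** Suppose stayers gain 5 points and intervention-arm leavers gain nothing. The model returns about 5.0 whether baseline-only men are kept or dropped. The as-randomised effect is 5 × (1 − 1/6) = 4.17 or 5 × (1 − 1/4) = 3.75. Week 9 PROMIS-29 from all leavers restores these values. From a random half it gives 5 × (1 − f)/(1 − f/2), where f is the share leaving, which is 4.55 or 4.29.

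**The case against.** The strongest reply is that the numbers are small and their inputs lean upwards. The table puts all early loss in one arm. D.3.1 allows 8 losses in total (48 to 40), across both arms and all visits, so 6 intervention-arm leavers before Week 5 would use three-quarters of that. Section H pays each participant by the week in either arm, which encourages staying. The trial is also described as preliminary. All of this stands, and it is why the point is minor. It does not defend the exclusion, which gains neither precision nor validity in these calculations.

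On D.6, nothing bars collecting PROMIS-29 from a man who withdraws, and anyone who gives a later score is no longer baseline-only and enters the model under G.4 as written. That also stands. Naming PROMIS-29 is an improvement, not the correction of an error.

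Two stronger readings are tempting, and the protocol supports neither:

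- A reader might combine the exclusion with the D.6 rule "If a participant withdraws before the second visit, they will be replaced" and infer that the two restrict the primary analysis to men who stayed to Week 5. D.6 adds participants and removes nobody from the analysis; only the G.4 sentence does that. A man who misses Week 5 but attends Week 9 is included. It is also not certain that the second visit means Study Visit 2, because D.5.1 counts the screening visit among the in-person visits.
- A reader might infer that the exclusion inflates the effect by removing men who would not have benefited. In that case the estimate is the same with or without them, so the inflation comes from missing later scores and not from this rule.

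**Conclusion.** The point holds as a minor one. G.4 makes an unexplained exception to its own account of the model and discards usable primary-outcome data from randomised men. Under the assumed SD and correlations, the bias runs from about zero (equal loss, or loss unrelated to baseline) to 0.60 points when loss is one-sided and mildly to moderately related to baseline. About 1.6 points, half a standard error, needs extreme one-sided loss driven by baseline. Keeping the men removes nearly all of this and costs nothing in precision. Two limits remain: loss that depends on unseen outcomes is not corrected, and men who leave during the washout have no PROMIS-29 score and stay outside the model under any wording.

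**What to change.** 1. In G.4, replace the exclusion with: *Every randomised participant with any PROMIS-29 score is included in the mixed model, in the group to which he was randomised.* This costs one sentence and needs no new data or participants.
2. Separately, add PROMIS-29 to the final data that D.6 seeks from men who withdraw. The cost is one more questionnaire for men who are already asked for saliva and laboratory samples. Of the two changes, only this one can address loss of men who would not have benefited, and only as far as those men respond.
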